8.3 Follow-Up Assessments

8.3.1 Immediate Post-Procedure Care, Observation, and Discharge

Subjects will be observed in the recovery area for as long as clinically appropriate after the termination of the procedure. To ensure that the unblinded endoscopist does not influence the care of a study subject, each participating endoscopist will have the option of implementing a provider-specific post-procedure order set that is **activated prior to randomization** and executed uniformly regardless of a subject's study group assignment. This order set may include intravenous fluid, analgesic, and antiemetic administration as well as parameters for hospital admission. If activated, all clinical decisions pertaining to the immediate post-procedure care of the subject and to hospital admission will be dictated primarily by this order set. If an order set is not available or has not been activated, the endoscopist will be responsible for designating a **blinded** clinician who will oversee the post-procedure care of the patient. In these cases, all post-procedure clinical decisions (including IVF and analgesic administration & the decision to admit to the hospital) will be dictated by this blinded healthcare provider. Once a patient is admitted, all clinical decisions will be made by an inpatient team that **cannot include the endoscopist** for at least 48 hours after the ERCP.

Performing endoscopists are permitted to communicate with patients and their families/friends after the procedure as long as they do not provide any direct or indirect information about treatment group assignment.

Performing endoscopists may ask that subjects be admitted to the hospital for observation or for additional post-procedure care depending on factors that occurred during the case which are unrelated to the study group assignment.

8.3.2 Post-Intervention Evaluations

A study coordinator will perform two follow-up contacts:

- 1) 3-5 days after the ERCP and,
- 2) 30 days after the ERCP.

The goal of the first follow-up is to ascertain those data necessary to adjudicate the primary endpoint. The goal of the second follow-up is to ascertain those data necessary to adjudicate the secondary outcome and assess for delayed serious adverse events. Permission to procure outside medical records (in the event a subject is admitted to a non-study center) will have been obtained at the time of consent.

Visit Windows: The timeline of the assessments is based on a start date of randomization. Although every attempt should be made to contact the subject at these pre-specified intervals, it is possible that the assessments may occur within a window around the intervals. The study data should always be collected regardless of its tardiness, however preferable windows are 3-5 days after ERCP for the first assessment, and 30 days +/- 5 days for the second assessment.

Subjects' medical records may be reviewed for up to 5 years after enrollment to review ERCP results, additional ERCP findings, hospitalizations, and laboratory or radiology data. Study samples (see below) and clinical data will be stored indefinitely as long as consent has not been withdrawn.

8.4 Biorepository

To improve our understanding of the mechanisms by which indomethacin protects against PEP, as well as to further explore the incompletely understood pathophysiology of PEP, we will establish a repository of whole blood, serum, plasma, urine, duodenal fluid, and stool specimens obtained from trial subjects on which future translational studies can be conducted.

Biologic specimens will be obtained from the first 1430 study subjects (original sample size) who agree to donate their samples. Subsequently, collection of specimens will be optional and dependent on a combination of individual site resources and subject consent. Specimen storage and tracking will be handled by the Clinical Ligand Assay Service Satellite (CLASS) Biosample Repository at the University of Michigan. The CLASS repository is a professionally managed biosample repository described in more detail in the “Resources and Environment” section and at: http://swan.class.sph.umich.edu/html/fn_classovr.htm. The samples will then be transferred in increments to the NIDDK Central Repository for long term storage.

Complete procedures for sample procurement, processing, labeling, storage, tracking, and sharing are detailed in the current version of the MoP available on WebDCU™.

8.5 ERCP Skills

An assessment of endoscopic skill and correlation with ERCP outcomes may be performed in a subset of subjects enrolled in SVI. The endoscopic and fluoroscopic footage of ERCP procedures in SVI subjects may be recorded. Participating endoscopists will each submit 5-20 videos of themselves performing complete ERCP procedures. The endoscopists will be asked to submit consecutive SVI cases, with at least 3 cases in which a biliary and/or pancreatic sphincterotomy is performed. After quality assurance of the footage and removal of all identifiers and non-critical footage, each video will be distributed to other endoscopists for peer rating. The correlation between endoscopic skill and adverse events will be examined to more concretely understand this relationship and to elucidate the composition of a skillful ERCP.

9.0 PROCEDURE FOR UNBLINDING

The medical safety monitor, clinical personnel treating the patient for the first 48 hours after ERCP, subject, and outcomes adjudicators are blinded to treatment assignment. Every effort should be made not to break the blind.

In the event of either an accidental or deliberate unblinding event, the clinical site individual who was unblinded must report the incident within one (1) calendar day of the unblinding in WebDCU™. The incident should not be discussed with other clinical site personnel.

In those cases of an emergency where the medical management of the subject would change based on the study procedure, emergency unblinding is authorized. Refer to the SVI MoP for emergency unblinding procedures.

10.0 DISCONTINUATION OF PARTICIPATION

10.1 Subject Withdrawal

The subject has the right to voluntarily withdraw from the study at any time for any reason without prejudice to his/her future medical care by the physician or at the institution.

If a subject withdraws consent, the date and reason for consent withdrawal should be documented. Subject data will be included in the analysis up to the date of the consent withdrawal.

A distinction should be made between subjects who fail to complete all forms on schedule or who miss some clinic visits and those who withdraw consent. Missed or rescheduled visits will be documented, but the subject will continue to be followed in the future according to protocol requirements, and all follow-up data will be included in the protocol-specified analysis.

10.2 Subject Removal from Study

Subjects may be removed from the study if any of the following events occur:

- (1) Significant protocol violation, either on the part of the subject or Investigator.
- (2) Refusal of the subject and/or the legal guardian to remain in the study (i.e. consent withdrawal).
- (3) If the physician or the Medical Safety Monitor believes it is in the subject's best interest to discontinue participation in the study.
- (4) Administrative reasons, e.g., MUSC or NIDDK termination of the study.

10.3 Procedure for Discontinuation

The procedure to be followed at the time a subject either discontinues participation or is removed from the study is:

- (1) Adverse event assessment.
- (2) Attempt to perform final follow-up evaluations.
- (3) Complete the End-of-Study form, including an explanation of why the subject is withdrawing or withdrawn.

10.4 Subject Lost to Follow-Up

All attempts to make contact with the subject will be documented in the study database. A plan of action for following up on subjects who cannot be contacted via telephone is outlined in the SVI Manual of Procedures. When all possible attempts to locate the subject have failed, that subject will be considered 'lost to follow up'.

10.5 Re-Entering the Study

If a subject who has withdrawn from the study voluntarily expresses interest in returning to complete the study, the subject can be re-entered.

10.6 Subject Transfers

Whenever a subject's medical care transfers to another clinical setting, every attempt must be made to obtain continued follow-up data and information on self-administered forms.

11.0 OUTCOMES DEFINITIONS

11.1 Primary

The primary endpoint is post-ERCP pancreatitis, based on consensus (Atlanta) guidelines:¹⁹ 1) New or increased pain in the upper abdomen **and** 2) amylase or lipase $\geq 3x$ the upper limit of normal 24 hours after the procedure **and** 3) hospitalization (or prolongation of existing hospitalization) for at least 2 days (at least the night of ERCP & following night).

Using these consensus guidelines as a diagnostic framework, three adjudicators will independently assess for the development of PEP based on review of a site-provided AE narrative and medical records for each study subject *hospitalized within 2 days after the ERCP*. The primary outcome will be adjudicated by an independent committee consisting of the MSM and two other voting members. To help the adjudicators assess post-procedure pain, the AE narrative and the pre and post-ERCP numeric pain scale results administered by the study coordinator will be available to the adjudicators. PEP will be declared if 2 of the 3 adjudicators determine that a subject has experienced post-ERCP pancreatitis. This committee-adjudicated outcome will be used for the primary analysis. Complete details of the outcomes adjudication process are available in the MoP.

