Primary Outcome Measure	The primary endpoint is post-ERCP pancreatitis, defined per consensus (Atlanta) criteria: 1) New or increased pain in the upper abdomen and 2) amylase or lipase $\geq 3x$ the upper limit of normal 24 hours after the procedure and 3) hospitalization (or prolongation of existing hospitalization) for at least 2 days (at least night of ERCP & next night). This outcome will be adjudicated by a blinded panel.
Statistical Analysis for Primary Outcome Measure	An intention-to-treat approach will be the primary basis for analysis of the primary outcome measure. The two-sided 95% upper confidence bound of the risk difference in the observed proportion of patients developing post-ERCP pancreatitis between the two treatment groups will be calculated.

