## 3. OUTCOME VARIABLES

### 3.1 Primary Efficacy Outcome

The primary outcome is a binary outcome variable measuring the post-ERCP pancreatitis event for each subject. Post-ERCP pancreatitis (PEP) is defined as: 1) New or increased pain in the upper abdomen and 2) amylase or lipase  $\geq 3x$  the upper limit of normal 24 hours after the procedure and 3) hospitalization (or prolongation of existing hospitalization) for at least 2 days (at least the night of ERCP & following night). These events must occur within 2 days of randomization in order to be considered PEP.

Using these consensus guidelines as a diagnostic framework, three adjudicators will independently assess for the development of PEP based on review of medical records and site-provided AE narrative for each study subject hospitalized within 2 days after the ERCP. PEP will be declared if at least 2 of the 3 adjudicators determine that a subject met all three components of the consensus diagnosis.

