**9.3 Secondary Outcome Variable Analysis**

Analysis of the secondary outcome, the proportion of subjects with moderate-severe PEP, will be analyzed in a similar manner as the primary outcome.

We also will examine the impact of pre-specified characteristics on the primary and secondary outcomes. Specifically, the goal of this analysis is to examine prognostic variables and their impact on the primary analysis. We also will explore subgroup populations for future hypothesis generation. The baseline variables that will be examined are: age (continuous), gender, race, body mass index (continuous), suspicion of sphincter of Oddi dysfunction, prior post-ERCP pancreatitis, history of recurrent pancreatitis, manometrically documented sphincter of Oddi dysfunction, difficult cannulation, pre-cut (access) sphincterotomy, pancreatic sphincterotomy, pancreatic acinarization, biliary sphincterotomy, pancreatic stent placement, double wire technique, make/model/length/caliber of pancreatic stent, trainee involvement, prophylactic stent characteristics, type of sphincter of Oddi dysfunction, and inpatient vs. outpatient status. The assessment of each of these variables will be conducted using a logistic regression model with the dichotomous primary outcome, PEP event. Treatment arm will be a main effect in the model and the above covariates examined. Each covariate will be assessed individually first with a model that includes interaction effect with the treatment. If a significant interaction is observed ( $p < 0.10$ ), then exploratory subgroup analyses will be considered. For each model, we will be looking at the parameter estimate of the covariate to examine its association with outcome. We also will be examining the parameter estimate of the treatment in the presence of the covariate. A multivariable model will be created based on the results of the individual models (a combination of statistical and clinical significance will be used for model inclusion). The final multivariable model will be based on goodness of fit criteria. For this final model, the adjusted risk difference will be estimated with a 95% confidence interval. If the upper limit of this confidence interval is 5% or greater, then non-inferiority of the treatments cannot be concluded in the presence of the particular covariates. This analysis will be run on both the ITT and PP analysis populations.

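### Read literally, pancreatitis first admitted after the night of ERCP fails the primary endpoint, yet both documents send it to adjudication and they declare an event by different rules

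*Protocol*

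**What the plan says.** Component 3 of the primary endpoint is a hospital stay, or prolongation of an existing one, "for at least 2 days (at least the night of ERCP & following night") in Protocol 11.1. The Protocol 1.0 summary has the same condition, "for at least 2 days (at least night of ERCP & next night"), and so does SAP 3.1. By contrast, the severity grades in Protocol 11.2 and SAP 3.2 count days only and name no starting night.

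The adjudication pool is wider. Both documents send to three adjudicators every subject "hospitalized within 2 days after the ERCP". Protocol 8.3.2 plans a contact at 3-5 days to collect the data for the primary endpoint, and adds: "Permission to procure outside medical records (in the event a subject is admitted to a non-study center") is obtained at consent.

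The declaration rules differ. Both documents introduce the criteria with "Using these consensus guidelines as a diagnostic framework". Protocol 11.1 then declares an event when two of three adjudicators judge that the subject had post-ERCP pancreatitis (PEP). SAP 3.1 requires that at least two of three "determine that a subject met all three components of the consensus diagnosis". SAP 3.1 also adds a time limit that Protocol 11.1 lacks: "These events must occur within 2 days of randomization in order to be considered PEP".

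**The concern.** The parenthesis makes the night of ERCP a minimum requirement. A patient discharged after the procedure and first admitted the next day with pain and raised enzymes cannot have spent that night in hospital. Under the SAP's rule that case is a non-event. Under the protocol's rule the adjudicators may count it.

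Such patients can exist. Protocol 8.3.1 treats admission as a decision made after the procedure, Protocol 8.3.2 anticipates admission to outside hospitals, and SAP 9.3 lists "inpatient vs. outpatient status" as a covariate. Their number is not given.

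Non-inferiority is judged against a fixed absolute margin of 5 points. If indomethacin alone is truly worse and a similar share of cases goes uncounted in both arms, the absolute difference shrinks in proportion and a false claim of non-inferiority becomes more likely.

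**Working it through.** **Inputs.** Margin 5% absolute and one-sided 2.5% level (Protocol 13.2); 9.7% event rate (Protocol 13.2, SAP 4.2); 650 per arm originally and 1090 per arm revised (Protocol 13.2, 1.0). The missed share is an assumption, shown from 0 to 30%.

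**The plan's own figure first.** With SE = sqrt[pC(1-pC)/n + pI(1-pI)/n] and D = pI - pC, the probability of claiming non-inferiority is Phi[(0.05 - D)/SE - 1.96].

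- 650 per arm, 9.7% in both: SE = sqrt(2 x 0.097 x 0.903/650) = 0.01642. Then 0.05/0.01642 - 1.96 = 1.086, so power is 86.1%, against 85% stated. Simulation also gives 86.1%.
- 650 per arm, 13% in both: 76.4%, against 76% in SAP 4.3.

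The method reproduces the plan.

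**Equal loss in both arms.** Let s be the share of true cases that the wording counts. The counted rates are s x 9.7% and s x 14.7%, so the true excess is exactly 5 points and the counted excess is 5s. With 1090 per arm:

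| Missed | Counted rates | Counted difference | SE | False non-inferiority |
|---|---|---|---|---|
| 0% | 9.70% v 14.70% | 5.0 | 0.01398 | 2.5% |
| 10% | 8.73% v 13.23% | 4.5 | 0.01336 | 5.6% |
| 20% | 7.76% v 11.76% | 4.0 | 0.01268 | 12.1% |
| 30% | 6.79% v 10.29% | 3.5 | 0.01195 | 24.1% |

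For 10% missed: (0.05 - 0.045)/0.01336 - 1.96 = -1.586, and Phi(-1.586) = 5.6%. Put another way, a true excess of 5/0.9 = 5.6, 5/0.8 = 6.3 or 5/0.7 = 7.1 points would be counted as 5.

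**Other base rates.** At 13% v 18%, using the threshold rate in SAP 4.3 for the control arm, the figures for 0, 10, 20 and 30% missed are 2.5, 5.2, 10.6 and 20.3%. If 9.7% is instead the control rate after the loss, and the counted excess is again 5s, they are 2.5, 5.5, 10.9 and 19.5%.

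**Unequal loss** (true 9.7% v 14.7%, 1090 per arm):

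- 20% missed with combination, 10% with indomethacin alone: 0.9 x 14.7 - 0.8 x 9.7 = 5.5 points; false non-inferiority 1.0%.
- 10% missed with combination, 20% with indomethacin alone: 0.8 x 14.7 - 0.9 x 9.7 = 3.0 points; false non-inferiority 32.9%.

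**The case against.** A reader might infer four stronger things, and the documents support none of them.

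- **That delayed admissions are definitely excluded.** The framework wording, the 2-day adjudication pool and the collection of outside records all suggest that they were meant to be considered. Protocol 11.1 leaves full adjudication details to the Manual of Procedures, which is not among the documents. If the manual counts these cases, few or none are lost. That stands. It does not cure the conflict between the two declaration rules, and the endpoint should be readable from the protocol and SAP.
- **That every same-day discharge is affected.** A patient who goes home and returns that same night still spends the required nights in hospital. Only a first admission after the night of ERCP is at issue.
- **That the SAP's 2-day limit requires the whole stay to finish within 2 days.** It reads more naturally as onset: SAP 2 speaks of pancreatitis within 2 days from randomisation, and SAP 3.2 grades stays of 4-10 and more than 10 days. The wording is loose, but it is not a second exclusion.
- **That the bias must favour non-inferiority.** It does so only if there is a true excess and the missed shares are similar. With no true difference an equal loss dilutes nothing, and the direction reverses if enough more cases are missed in the combination arm.

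Two further cautions stand. The error is false only against an endpoint that counts delayed admissions; for the endpoint exactly as written it stays at 2.5%. And a control rate of about 16.5% could be back-solved from the revised sample size (2180/1.1, or about 991 per arm, at 85% power), but the documents never state it and it would already reflect cases as currently counted. It is not used here.

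**Conclusion.** The point holds as an unresolved inconsistency in the primary endpoint. Protocol 1.0, Protocol 11.1 and SAP 3.1 define a stay that a first admission after the night of ERCP cannot satisfy, while both documents adjudicate such admissions and apply different tests to them. Applied as the SAP states it, the rule would drop real pancreatitis cases from a trial with an absolute margin.

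The size is unknown because the documents give no share of late admissions. If 10% of cases are missed equally in both arms and the true excess is 5 points, the false-claim rate roughly doubles, from 2.5% to 5.6%. Those two conditions are assumptions, and a differential loss can move the result either way. This is worth correcting, but it does not show that the trial is biased.

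**What to change.** Reconcile Protocol 1.0, Protocol 11.1 and SAP 3.1 with the 2-day adjudication window:

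1. Define component 3 as at least two nights in hospital after ERCP, either as a new admission starting within 2 days after ERCP or as prolongation of an existing stay.
2. State that the SAP's 2-day limit applies to onset or admission, not to completion of the stay.
3. Use the same declaration rule in both documents, and instruct the adjudicators accordingly.
4. Make the change blinded to arm, with a blinded re-check of delayed admissions already in the adjudication pool.
5. Report by arm the number of pancreatitis cases first admitted after the night of ERCP, and repeat the primary comparison with these cases counted and not counted.

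The cost is a late clarification of primary endpoint wording, after the first interim analysis and the sample size increase, plus a small re-adjudication effort. No new patients are needed, because these cases are already in the adjudication pool.

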11.2 Secondary

The secondary endpoint is moderate-severe post-ERCP pancreatitis, also defined on the basis of consensus guidelines: mild PEP is defined as pancreatitis that results in hospitalization (or prolongation of existing hospitalization) for ≤ 3 days. Moderate PEP – pancreatitis that results in hospitalization (or prolongation of existing hospitalization) for 4-10 days. Severe PEP – pancreatitis that results in hospitalization (or prolongation of existing hospitalization) for > 10 days, or leads to the development of a pancreatic fluid collection, or requires additional endoscopic, percutaneous, or surgical intervention. This outcome will also be adjudicated by the independent panel. Subjects may be unblinded to study group assignment after 7 days (if they receive notification for pancreatic stent follow-up), and thus the study is only partly double-blinded for the secondary endpoint.

12.0 DATA COLLECTION, MANAGEMENT, AND QUALITY CONTROL PROCEDURES

Comprehensive data coordinating functions for this clinical trial, including clinical monitoring, database development, web-based data entry and management, as well as the creation and export of study reports for the data and safety monitoring board (DSMB) will be provided by the SDMC at MUSC.

12.1 Data Management

Data management will be handled by the SVI SDMC which is housed in the Data Coordination Unit (DCU) in the Department of Public Health Sciences at the Medical University of South Carolina (MUSC). All study activities will be conducted in coordination with the study PI, the clinical sites, and NIDDK, and will use an electronic data acquisition method where all clinical data on randomized subjects will be entered by the site personnel in real time. The latest version of each CRF will be available as a PDF file on the study website for use as worksheets and source documents by study personnel.

The study data will be managed (including data queries) by the SDMC using the WebDCU™ system. This user-friendly web-based database system, developed by the DCU, will be used for regulatory document management, subject randomization, data entry, data validation, project progress monitoring, subject tracking, site monitoring, user customizable report generation and secure data transfer.

Upon entry of CRFs into the study database, quality control procedures will be applied at each stage of data handling in order to ensure compliance with GCP guidelines, integrity of the study data, and document processing system reliability.

All sites will be monitored by the SDMC and site monitors will conduct periodic site visits to review source documents and case report form information. A quality assurance record audit will be implemented. Audit findings will be used to identify and correct problems.

